16.3 Phase Ib portion

The phase Ib portion of this trial consists of an expansion cohort of patients with metastatic disease from pancreatic adenocarcinoma who have received no more than 1 line of prior therapy in the metastatic setting. Patients will be separated into two cohorts based on their HRD status (section 5).

- 16.31 Analysis plans: All the relevant results pertaining to toxicity, MTD, laboratory correlates will be examined in an exploratory and hypothesis-generating fashion.
- 16.32 Disease control (DC) is defined as achieving CR, PR, or maintaining SD (per RECIST v1.1) as the tumor assessment result for at least 24 weeks. Disease Control Rate will be estimated by the number of evaluable patients achieving disease control divided by the total number of evaluable patients. Evaluable patients for the primary endpoint are defined as who have signed the consent form, are eligible, received any protocol treatment. Point estimates will be generated for disease control rates within each cohort along with 95% binomial confidence intervals. (Clopper, C.J and E.S. Pearson, *The Use of Confidence or Fiducial Limits Illustrated in the Case of Binomial*. *Biometrika*, 1934.**26**(4).: p. 404-413).

16.4 Phase II portion

The phase II portion will include a safety run-in to assess whether there is unacceptable toxicity in the first 6 patients accrued (BRCA1/2 and PALB2, and other HRD together) without halting the trial. The phase II portion will use a 2-stage Simon design and an interim analysis with relaxed probability of stopping for futility to assess the efficacy of MFR in patients with untreated pancreatic cancer with BRCA1/2 and PALB2. Patients with untreated pancreatic cancer with HRD other than BRCA1/2 and PALB2 will be accrued for exploratory analysis. The recommended dose level determined in the phase I portion of the trial will be used as the starting dose for Phase II.

16.41 Primary Endpoint

The primary endpoint for the phase II portion of the trial will be the best response rate at 32 weeks, which is defined as the number of patients who had response ≤ 32 weeks of registration divided by the number of evaluable patients. Response is defined as either complete response (CR) or partial response (PR), per RECIST 1.1.

16.42 Decision Rule

The largest success proportion (proportion of evaluable patients with CR/PR) where the proposed treatment regimen would be considered ineffective in this population is 23% (Von Hoff et. al., 2013²⁹ and Conroy et. al., 2011³⁰), and the smallest success proportion that would warrant subsequent studies with the proposed regimen in this patient population is 45%.

Evaluable patients for the primary endpoint are defined as patients with HRD encompassing BRCA1, BRCA2, and PALB2 deleterious mutations (germline and somatic), consented, eligible, and received any protocol treatment. The following two-stage Simon's design and an interim analysis with relaxed probability of stopping for futility uses a minimum of 11 and a maximum of 21 patients to test the null hypothesis that the true success proportion in a given patient population is at most 23%. The current design assumes a one-sided alpha level 0.1 and 80% power. The above power calculation was done using Simon's like design with relaxed futility stopping (Ivanova A.) and assumes a one-sided alpha level 0.1, 80% power, and lower and upper bound for the probability of stable disease (SD) to be 0.1 and 0.2, respectively.

16.421 STAGE 1

Among first 11 patients enrolled into study, if 2 or fewer patients with CR/PR/SD are observed ≤ 16 weeks after registration, we will consider this regimen ineffective in this patient population and terminate the study. Otherwise, if at least 3 patients with CR/PR/SD are observed ≤ 32 weeks after registration, we will proceed to Stage 2 and continue accrual.

16.422 STAGE 2

The regimen will be considered ineffective if either enrollment is

discontinued after stage 1 or if 7 or fewer patients with CR/PR are observed in the first 21 evaluable patients. This regimen will be considered promising if 8 or more patients with CR/PR are observed in the first 21 evaluable patients.

16.423 Over Accrual

If more than the target number of patients are accrued, the additional patients will not be used to evaluate the stopping rule or used in any decision-making process. Analyses involving over accrued patients are discussed in Section 16.5.

16.424 Operating characteristics

The probability of declaring that this regimen warrants further studies (i.e. statistical power) under various success proportions and the probability of stopping accrual after the first stage can be tabulated as a function of the true success proportion as shown in the following table (based on simulation study with 10,000 replicates).

If the true success proportion is ...	0.23	0.30	0.35	0.40	0.45
Then the probability of declaring that the regimen warrants further study is...	8.34%	27.60%	45.43%	65.77%	79.69%
And the probability of stopping at stage 1 is	12.12%	9.67%	5.44%	1.20%	0.58%

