16.12 Sample Size

The phase I portion of this study is expected to require a minimum of 49 patients and a maximum of 58 patients including 40 patients who will be accrued into the expanded phase Ib cohort (see below).

The phase Ib portion of this trial consists of 2 expansion cohorts of patients adenocarcinoma who have received no more than 1 line of prior therapy in the metastatic setting. The objective of the phase Ib study is exploratory and hypothesis generating in nature. The phase 1b analysis is not powered; thus, no sample sizes were derived. We plan to enroll 40 patients to the Phase Ib, including 28 patients with either unknown mutation status or non-HRD (known wildtype for BRCA1, BRCA2, and PALB2 genes) and 12 patients with known HR deficiency (known mutation in either BRCA1, BRCA2, or PALB2 genes) with the intent of establishing the efficacy of rucaparib in combination with nal-IRI. In addition to 12 patients with known HR deficiency due to mutations in BRCA1, BRCA2, or PALB2, we expect that 7 of 28 Unknown/Non-HRD cohort patients will have HR deficiency since 25% of PDAC patients have defects in DNA repair.

The phase II portion of this study is expected to require a minimum of 11 and a maximum of 21 untreated pancreatic patients with HRD encompassing BRCA1, BRCA2, or PALB2 deleterious mutations (germline and somatic). An additional 3 patients with untreated pancreatic cancer and with BRCA1, BRCA2 or PALB2 deleterious mutation will be accrued to account for ineligibility, cancellation, major treatment violation, or other reasons. We anticipate accruing patients with

other HRD (other than BRCA1, BRCA2, or PALB2) during the phase II portion of the trial for exploratory analysis. Therefore, the phase II portion is expected to screen 200 patients and accrue 24 patients with HRD encompassing BRCA1, BRCA2 and PALB2 patients and another 28 patients with other HRD with an overall sample size will be a maximum of 52 patients.

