16.52 Adverse Event Stopping Rules

The stopping rules specified below are based on the knowledge available at study development. We note that the Adverse Event Stopping Rule may be adjusted in the event of either (1) the study reopening to accrual or (2) at any time during the conduct of the trial and in consideration of newly acquired information regarding the adverse event profile of the treatment(s) under investigation. The study team may choose to suspend accrual because of unexpected adverse event profiles that have not crossed the specified rule below.

16.521 Phase I/Ib Adverse Event Stopping Rule

During the first 2 cycles, 4 of the initial 10 treated patients or 40% or more of all patients (i.e., when accrual is greater than 10 patients) have experienced a Grade 4+ adverse event at least possibly related to study treatment, per NCI Common Terminology Criteria for Adverse Events v.5.0, excluding the following:

- Grade 4 neutrophil count decreased lasting ≤ 7 days
- Grade 4 white blood cell decreased lasting ≤ 7 days
- Grade 4 platelet count decreased lasting ≤ 7 days
- Grade 4 diarrhea responding to optimal support

16.522 Phase II Adverse Event Stopping Rules

Accrual will be temporarily suspended to this study if at any time we observe events considered at least possibly related to study treatment (i.e. an adverse event with attribute specified as “possible”, “probable”, or “definite”) that satisfy either of the following:

- If 1 or more patients out of the first 6 patients (either HRD encompassing BRCA1, BRCA2, PALB2 or other HRD) experience grade 5 events (death) deemed at least possible (possible, probably, or definite) related to MFR, the accrual to the study will be suspended to allow for investigation. After consideration by the study team (study chair, statistician) and consultation with the sponsor, a decision will be made as to whether accrual can be resumed.
- If 6 or more patients among the first 20 patients (either HRD encompassing BRCA1, BRCA2, PALB2 or other HRD) enrolled

or 30% of the patients thereafter develop a grade4+ non-hematologic toxicities at least possible (possibly, probably or definitely) related to treatment, enrollment will be suspended so that the adverse event data can be examined and a trial recommendation will be formulated and presented to Mayo DSMB.

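### The phase II stage-1 stopping row depends on an unstated stable-disease rate that differs by column, and the stage-1 rule uses two time windows and a different patient count from stage 2

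*Combined protocol and SAP*

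**What the plan says.** Section 16.42 tests a response rate of 23% against 45% at one-sided alpha 0.1 with 80% power. It uses a two-stage design with relaxed futility stopping and sets the "lower and upper bound for the probability of stable disease (SD) to be 0.1 and 0.2". No SD rate is given for any particular scenario.

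The stage-1 stop sentence in 16.421 begins "Among first 11 patients enrolled into study, if 2 or fewer patients with CR/PR/SD are observed ≤ 16 weeks after registration". The proceed sentence follows, introduced by *Otherwise*, and applies "if at least 3 patients with CR/PR/SD are observed ≤ 32 weeks after registration". In 16.422 the regimen is ineffective "if 7 or fewer patients with CR/PR are observed in the first 21 evaluable patients". Section 16.42 defines evaluable as carrying a BRCA1, BRCA2 or PALB2 deleterious mutation, consented, eligible and having received any protocol treatment.

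Section 16.424 says that "the probability of stopping accrual after the first stage can be tabulated as a function of the true success proportion". The table, from 10,000 simulated trials, prints:

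| True response rate | 0.23 | 0.30 | 0.35 | 0.40 | 0.45 |
|---|---|---|---|---|---|
| Declared promising | 8.34% | 27.60% | 45.43% | 65.77% | 79.69% |
| Stopped at stage 1 | 12.12% | 9.67% | 5.44% | 1.20% | 0.58% |

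**The concern.** The stage-1 rule counts stable disease as well as response, so the chance of stopping is a function of two rates. A row indexed by one of them has a meaning only if the other is stated. The printed row is also oddly shaped: it falls little from 0.23 to 0.30 and then sharply from 0.35 to 0.40.

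This row is the plan's only description of how often the look would end accrual to an ineffective regimen. A monitoring board would take 12% from it when the plan's own inputs allow anything from about 8% to 24%.

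The wording of the rule leaves two further questions open: which assessment window decides, and whether a registered patient who is ineligible or never treated counts among the 11. A binding stopping rule should not need interpretation on either.

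**Working it through.** **Inputs.** Stage 1: n = 11, stop at 2 or fewer with CR/PR/SD (16.421). Stage 2: 8 or more CR/PR among 21 (16.422). Response rates p and 10,000 replicates (16.424). SD rate s between 0.1 and 0.2 (16.42). I take p + s as the chance that a patient counts as CR/PR/SD at the look.

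**Step 1: the declare-promising row.** For each stage-1 outcome (trinomial in CR/PR, SD, other) that does not stop, multiply by the binomial probability of reaching 8 CR/PR with the 10 stage-2 patients.

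| p | 0.23 | 0.30 | 0.35 | 0.40 | 0.45 |
|---|---|---|---|---|---|
| Printed | 8.34% | 27.60% | 45.43% | 65.77% | 79.69% |
| Exact, s = 0.15 | 8.7% | 27.6% | 46.2% | 64.9% | 80.2% |

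All five agree within 95% simulation error. Over s = 0.10 to 0.20, alpha runs from 8.65% to 8.74% and power from 80.0% to 80.3%. The model and cut-offs are therefore read as the plan intended.

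**Step 2: the stopping row.** P(stop) = P(X ≤ 2), with X ~ Binomial(11, p + s). At p = 0.23:
- s = 0.10: 0.67^11 + 11 × 0.33 × 0.67^10 + 55 × 0.33² × 0.67^9 = 0.0122 + 0.0662 + 0.1630 = 24.1%.
- s = 0.20: 0.57^11 + 11 × 0.43 × 0.57^10 + 55 × 0.43² × 0.57^9 = 0.0021 + 0.0171 + 0.0646 = 8.4%.

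| p | 0.23 | 0.30 | 0.35 | 0.40 | 0.45 |
|---|---|---|---|---|---|
| Printed | 12.12% | 9.67% | 5.44% | 1.20% | 0.58% |
| s = 0.10 | 24.1% | 11.9% | 6.5% | 3.3% | 1.5% |
| s = 0.20 | 8.4% | 3.3% | 1.5% | 0.6% | 0.2% |
| Best single s (about 0.139) | 16.6% | 7.5% | 3.9% | 1.8% | 0.7% |
| s uniform on 0.1–0.2 | 15.3% | 6.9% | 3.5% | 1.6% | 0.7% |
| s that fits the printed cell | 0.168 | 0.118 | 0.114 | 0.162 | 0.151 |
| 95% simulation limits for that s | 0.164–0.173 | 0.113–0.123 | 0.108–0.120 | 0.153–0.173 | 0.139–0.166 |

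The best single s, by minimum chi-square, leaves a chi-square of 303 on 4 degrees of freedom. It misses the first four columns by 12.2, 8.1, 8.2 and 4.5 simulation standard errors. The uniform average misses them by 8.8, 11.0, 10.5 and 3.4. The limits for s at p = 0.30 and 0.35 do not overlap those at 0.23, 0.40 and 0.45.

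The ratios between columns show the same thing. From p = 0.23 to 0.30 the printed ratio is 9.67/12.12 = 0.80, against 0.49 at s = 0.10 and 0.39 at s = 0.20. From 0.35 to 0.40 it is 1.20/5.44 = 0.22, against 0.50 and 0.40.

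**Step 3: expected sample size at 23% response.** E(N) = 21 − 10 × P(stop): 19.8 from the printed value, 18.6 at s = 0.10 and 20.2 at s = 0.20.

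**Step 4: the two windows.** Three patients counted by week 16 are also counted by week 32. If *Otherwise* is read strictly, the 16-week sentence decides and the 32-week clause adds nothing. If the 32-week clause is a live criterion, a trial with 2 or fewer by week 16 and 3 or more by week 32 satisfies both sentences, and they point opposite ways.

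**Step 5: enrolled against evaluable.** Section 16.12 provides for such losses: "An additional 3 patients with untreated pancreatic cancer and with BRCA1, BRCA2 or PALB2 deleterious mutation will be accrued to account for ineligibility", among other reasons. That is 3 of 24, or 11 × 3/24 = 1.4 of the first 11. If one of the 11 is non-evaluable and cannot contribute CR/PR/SD (a worst case), P(stop) becomes P(X ≤ 2) with X ~ Binomial(10, p + s):

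| | 11 contribute | 10 contribute |
|---|---|---|
| p = 0.23, s = 0.10 | 24.1% | 30.7% |
| p = 0.23, s = 0.20 | 8.4% | 12.4% |
| p = 0.45, s = 0.10 | 1.5% | 2.7% |
| p = 0.45, s = 0.20 | 0.2% | 0.5% |

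**The case against.** The strongest reply is that the plan assumes a range for SD, not a constant, and that all five implied rates lie inside it. That stands. An SD rate that varied by column would fit every cell, and the documents do not show how the cited design tool uses the bounds. A reader might infer from the size of the misses that the row is impossible or that the design was miscalculated. The documents do not support that: the declare-promising row reproduces, and alpha, power, the 11/21 sample sizes and the cut-offs hold across the SD range. What remains is that the input driving the row is unstated and not constant.

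A reader might also infer that patients with other HRD enter the first 11. Phase II plans "another 28 patients with other HRD with an overall sample size will be a maximum of 52 patients", and the safety rule in 16.522 applies to "If 6 or more patients among the first 20 patients (either HRD encompassing BRCA1, BRCA2, PALB2 or other HRD) enrolled". But Section 16.12 defines the 11 and the 21 as BRCA1/2/PALB2 patients, and Section 16.4 confines the two-stage design to them, with other HRD accrued for exploration. Where the plan pools the groups, as in 16.522, it says so; 16.421 does not.

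A third tempting reading is that the 32-week clause routinely delays the decision while stage-2 patients accrue. It would do so only if that clause governs, fewer than three patients qualify by week 16, and accrual is not paused. *Otherwise* favours the 16-week sentence, so no count of extra patients is claimed.

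Finally, the non-evaluable calculation is an upper case. An ineligible but treated patient can still respond or have stable disease, and the change is then smaller.

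**Conclusion.** Minor, with high confidence. As printed, the stopping row is not a function of the response rate and cannot be checked against any SD rate that the plan states. Its 12.1% at 23% response stands in for a range of 8.4% to 24.1%. This rests on the exact binomial model with p + s as the chance of counting at the look; the same model reproduces the row above it.

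The 16-week and 32-week sentences conflict, or one of them is redundant. Counting enrolled patients at stage 1 lets ineligible or untreated BRCA1/2/PALB2 patients into the futility count. At 23% response the worst-case effect of one such patient is 4.0 to 6.6 percentage points (12.4 − 8.4 and 30.7 − 24.1). None of this alters the final decision rule.

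**What to change.** 1. In 16.424, replace the stopping row with exact rows labelled by SD rate, for response 0.23/0.30/0.35/0.40/0.45: SD 0.10, 24.1/11.9/6.5/3.3/1.5%; SD 0.20, 8.4/3.3/1.5/0.6/0.2%. Stating the SD rate used in each existing column would make the row checkable, but would still hide the range at each response rate.
2. In 16.421, reconcile the stop and proceed sentences so that one window governs the stage-1 count.
3. In 16.421, count the first 11 *evaluable* patients, using the definition already in 16.42, to match stage 2.

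The cost is SAP wording and one recomputed row, with no extra patients and no change to cut-offs, alpha or power. The one drawback is that the stopping probability becomes a range instead of a single figure. The changes should be made before the stage-1 look.

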16.43 Phase II Analysis Plan

16.431 Primary Endpoint Analysis - Estimation: The proportion of best response ≤ 32 weeks will be estimated by the number of evaluable patients who reach CR/PR, per RECIST 1.1, ≤ 32 weeks since registration divided by the total number of evaluable patients. Confidence intervals for the proportion will be calculated according to the approach of Duffy and Santner (1987).

16.432 Secondary Endpoint Analyses

16.432a Overall survival: Survival time is defined as the time from registration to death due to any cause. Patients who fail to return for evaluation after beginning therapy will be censored for survival on the last day of therapy or date last known to be alive, whichever is later. The distribution of survival time will be estimated using the method of Kaplan-Meier (1958).

16.432b Progression-free survival: Progression-free survival is defined as the time from registration to the earliest date documentation of disease progression or death due to any cause. Patients who fail to return for evaluation after beginning therapy will be censored for progression on the last day of therapy or date last known to be alive, whichever is later. The distribution of progression-free

survival will be estimated using the method of Kaplan-Meier (1958).

16.432c Toxicity: As per NCI CTCAE version 4.03, the term toxicity is defined as adverse events that are classified as either “possibly,” “probably,” or “definitely related” to study treatment. The maximum grade for each type of toxicity will be recorded for each patient, and frequency tables will be reviewed to determine toxicity patterns within patient groups. In addition, we will review all adverse event data that is graded as 3, 4, or 5 and classified as either “unrelated” or “unlikely to be related” to study treatment in the event of an actual relationship developing. Adverse events and toxicities will be evaluated using all patients who have received any study treatment as well as summarizing those who have been included in the efficacy analyses. The overall adverse event rates for grade 3 or higher adverse events will be compared using Chi-Square or Fisher’s Exact tests between the two treatment groups.

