6. Dose-escalation phase I, ECG should be done on baseline and Cycle 2, Day 1, measured twice at least 5 minutes apart. For Phase Ib and II – ECG should be done prior to cycle 1 only, then as indicated.
7. Any Adverse event assessment within 30 days of end of treatment will be recorded on the adverse event assessment form in the last cycle of treatment.
8. Treatment decision/patient care for patients who are off protocol treatment is at the discretion of the treating physician. The observation period is recommended by the study protocol but no data collection is required other than adverse event assessment (See Footnote 7)

R Research funded (see Section 19.0)

Event Monitoring: Patients will be followed for survival every 6 months for 3 years from registration. This can be done via a phone call to the patient and does not require the patient to return to the consenting site.

5.0 Grouping Factors:

- Phase I (Dose Escalation)- pancreatic vs.
- Phase I (Dose Escalation)- colorectal vs.
- Phase I (Dose Escalation)- gastroesophageal vs.
- Phase I (Dose Escalation)- biliary tract vs.
- Phase Ib (Dose Expansion)-pancreatic, Unknown/non-HRD patients vs.
- Phase Ib (Dose Expansion)-pancreatic, HRD patients vs.
- Phase II.

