7.0 Protocol Treatment

7.1 Treatment Schedule – Use actual weight with dose adjustments if weight changes more than 10% from baseline.

Cycle = 28 days

Agent	Route	Day
Nanoliposomal Irinotecan (nal-IRI)	IV	Days 1 and 15
Leucovorin (LV)*	IV	Days 1 and 15, prior to 5-FU
Fluorouracil (5-FU)	IV	Days 1 and 15
Rucaparib	PO	Twice each day on Days 4-13 and Days 18-27 of a 28 day cycle.

*If there is a shortage of leucovorin (LV) in the U.S., and you are unable to obtain access, LV may be held until supply is available. LV will not be administered in the phase Ib/II portion of the study

7.11 Planned Phase I Dose Escalation Levels:

Dose Level	Agent	Dose	Route	Day
DL-2	Nanoliposomal irinotecan (nal-IRI)	43 mg/m2	Intravenous over 90 minutes	Days 1 and 15
	Leucovorin (LV)	400 mg/m2	Intravenous	Days 1 and 15, prior to 5-FU
	Fluorouracil (5-FU)	2000 mg/m2	Intravenous over 46 hours	Days 1 and 15
DL-1	Rucaparib	200 mg	Oral	Twice daily on Days 4-13 and 18-27
	nal-IRI	50 mg/m2	Intravenous over 90 minutes	Days 1 and 15
	LV	400 mg/m2	Intravenous	Days 1 and 15, prior to 5-FU
	5-FU	2400 mg/m2	Intravenous over 46 hours	Days 1 and 15
DL1*	Rucaparib	200 mg	Oral	Twice daily on Days 4-13 and days 18-27
	nal-IRI	50 mg/m2	Intravenous over 90 minutes	Days 1 and 15
	LV	400 mg/m2	Intravenous	Days 1 and 15, prior to 5-FU
	5-FU	2400 mg/m2	Intravenous over 46 hours	Days 1 and 15
DL2-A	Rucaparib	400 mg	Oral	Twice daily on Days 4-13 and days 18-27
	Nanoliposomal irinotecan (nal-IRI)	50 mg/m2	Intravenous over 90 minutes	Days 1 and 15
	Fluorouracil (5-FU)	2400 mg/m2	Intravenous over 46 hours	Days 1 and 15
DL 2-B	Rucaparib	600 mg	Oral	Twice daily on Days 4-13 and days 18-27
	nal-IRI	70 mg/m2	Intravenous over 90 minutes	Days 1 and 15
	LV	400 mg/m2	Intravenous	Days 1 and 15, prior to 5-FU
	5-FU	2400 mg/m2	Intravenous over 46 hours	Days 1 and 15
DL 3	Rucaparib	400 mg	Oral	Twice daily on Days 4-13 and days 18-27
	nal-IRI	70 mg/m2	Intravenous over 90 minutes	Days 1 and 15
	Leucovorin	400 mg/m2	Intravenous	Days 1 and 15, prior to 5-FU
	5-FU	2400 mg/m2	Intravenous over 46 hours	Days 1 and 15
	Rucaparib	600 mg	Oral	Twice each day on

				Days 4-13 and days 18-27
--	--	--	--	--------------------------

* Starting dose level

Only patients with pancreatic, colorectal, gastroesophageal and biliary tract cancers will be included

7.12 Phase Ib Dose Expansion (Phase Ib Study at recommended dose level determined by the Phase I portion):

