13.0 Treatment/Follow-up Decision at Evaluation of Patient

13.1 Patients who are CR, PR, or SD will continue treatment per protocol. Patients who are CR, PR, or SD at time of their reassessment and **have not** experienced intolerable toxicity will be allowed to continue protocol treatment at the same dose level until PD or maximum of 3 years whichever is earlier.

Those patients who are CR, PR, or SD but **have** experienced unacceptable toxicity may be eligible for retreatment at a lower dose until PD or maximum of 3 years whichever is earlier, at discretion of treating physician (see Section 8.0).

13.2 Patients who develop PD while receiving therapy will go to the event-monitoring phase. Treatment decision during event-monitoring phase is at the discretion of the treating physician.

13.3 Patients who go off protocol treatment for reasons other than PD will go to the event-monitoring phase per Section 18.0. Treatment decision during event-monitoring phase is at the discretion of the treating physician.

13.4 If a patient enrolled to Phase I dose escalation part of the study fails to complete the initial course of therapy (defined as drug administration \leq 75% of expected cycle 1 total dose) for reasons other than dose-limiting toxicity defined adverse events, the patient will be regarded as uninformative in regard to the primary study goal and an additional patient will be enrolled at the current dose level

13.5 A patient is deemed *ineligible* if after registration, it is determined that at the time of registration, the patient did not satisfy each and every eligibility criteria for study entry. The patient may continue treatment off-protocol at the discretion of the physician as long as there are no safety concerns, and the patient was properly registered. The patient will go directly to the event-monitoring phase of the study (or off study, if applicable).

- If the patient received treatment, all data up until the point of confirmation of ineligibility must be submitted. Event monitoring will be required per Section 18.0 of the protocol.
- If the patient never received treatment, on-study material must be submitted. Event monitoring will be required per Section 18.0 of the protocol.

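### Section 16.432b censors PFS by the overall-survival rule, at a date that is not a tumour assessment, so unscanned time counts as progression-free

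*Combined protocol and SAP*

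**What the plan says.** Section 16.432b counts documented progression or death from any cause as the PFS event and estimates PFS by Kaplan-Meier. Its only censoring sentence begins "Patients who fail to return for evaluation after beginning therapy will be censored for progression". On the date, it says that these patients "will be censored for progression on the last day of therapy or date last known to be alive, whichever is later". For overall survival, 16.432a says that the same patients "will be censored for survival on the last day of therapy or date last known to be alive, whichever is later". The two rules differ only in the word for the endpoint.

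Four other places bear on how far these dates can fall from a scan:

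- Sections 4.0 and 11.1 schedule imaging every 8 weeks, before cycle 3 and each later odd cycle, plus a tumour measurement at end of treatment.
- Section 7.1 gives rucaparib "Twice each day on Days 4-13 and Days 18-27 of a 28 day cycle", so the last treatment day can come well after the last scan.
- Section 13.3 says "Patients who go off protocol treatment for reasons other than PD will go to the event-monitoring phase per Section 18.0".
- For event monitoring, section 4.0 says "Patients will be followed for survival every 6 months for 3 years from registration" and adds "This can be done via a phone call to the patient and does not require the patient to return to the consenting site".

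No section ties PFS censoring to the date of a tumour assessment, and 16.432b gives no rule for patients still progression-free at data cut-off.

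**The concern.** For overall survival the rule is right, because a patient known to be alive is known to be event-free. For PFS that does not follow: a telephone contact shows survival but not tumour status. Under the rule as written, a patient who was last scanned at month 4 and reached by telephone at month 12 adds eight months of progression-free time that nobody observed.

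PFS is a named secondary aim (2.32) in a single-regimen Phase II, so no concurrent control arm shares the bias. An upward shift from the censoring date is also not reflected in a confidence interval.

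The documents do not say whether failing to return covers patients in event monitoring. Left open, both that question and the choice of date would be settled after the data are seen.

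**Working it through.** **No plan figure to reproduce.** The documents give no PFS estimate, landmark, benchmark or test.

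**Direction.** For the same events, later censoring dates only add patients to the risk set. Example: one event among 6 patients under scan gives 1 - 1/6 = 0.833. Keeping 2 alive but unscanned patients at risk gives 1 - 1/8 = 0.875.

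**Last treatment day against last scan.** Cycle 3 day 1 is study day 2 x 28 + 1 = 57. Cycle 4 day 27 is study day 3 x 28 + 27 = 111. The gap is 111 - 57 = 54 days.

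**Size, by simulation (600,000 patients).**

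From the documents:
- Scans every 8 weeks (11.1), an exit scan (4.0) and contact every 6 months (4.0).
- Follow-up of 36 months (4.0, 18.1). Alternatively, 16.13 gives at least 4 months after the last accrual and an accrual period of 12 to 24 months. That means 4 to 4 + 12 = 16 months, or 4 to 4 + 24 = 28 months.

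Assumed:
- Exponential progression and post-progression survival, median 6 months each; death dates known.
- 10, 20 or 30% assigned to leave imaging, with four leaving-time distributions: uniform over 0-6 months, uniform over 0-12 months, exponential with median 6 months, or a uniform fraction of the time to detected progression or death.
- Capture, meaning the share of leavers whose disease status stays documented, of 0, 50 or 80%.
- 12-month PFS as the landmark.

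Complete imaging gives 27.8%. The plan's rule minus last-assessment censoring, in percentage points:

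| Follow-up | 80% capture | 50% capture | No capture |
|---|---|---|---|
| 36 months | 0.0-0.3 | 0.1-0.7 | 0.2-1.3 |
| 4-28 months | 0.2-1.2 | 0.6-2.9 | 1.1-5.7 |
| 4-16 months | 0.3-1.4 | 0.7-3.5 | 1.4-7.2 |

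The 7.2 needs 30% assigned to leave, leaving within 6 months, no capture and the shortest follow-up: 31.7 - 24.5 = 7.2. For patients truly lost (no exit scan, no later contact) the effect is 0.01-0.09 points. The median is 7.2-8.0 months in all these scenarios, against 7.4 with complete imaging.

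**Which rule is nearer to 27.8%?** With 20% assigned and leaving uniform over 0-6 months, 12-month PFS (%) under the plan / last assessment / last assessment with late deaths also censored:

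| Follow-up | 80% capture | 50% capture | No capture |
|---|---|---|---|
| 36 months | 28.7 / 28.5 / 27.7 | 30.1 / 29.6 / 27.4 | 32.4 / 31.6 / 27.0 |
| 4-28 months | 28.2 / 27.4 / 27.3 | 29.5 / 27.6 / 27.2 | 31.7 / 27.9 / 27.0 |
| 4-16 months | 27.2 / 26.3 / 26.5 | 28.3 / 26.1 / 26.7 | 30.3 / 25.7 / 27.0 |

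**Wider grid of assumptions (320 scenarios).** Median PFS was 4-10 months, post-progression survival 4 or 8 months, loss about 5-30%, and contact after loss 1-36 months.

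- Both 6- and 12-month PFS move by 3 points or less in 77% of scenarios, and the median is unchanged in 87%.
- With at most 10% lost, the largest shifts are 3.7 points (6 months) and 4.6 points (12 months).
- With 30% lost, unrelated to progression, they reach 11.0 and 13.6 points, and the median moves by up to 1.8 months.
- With loss at progression, the 12-month difference runs from -5.5 to +4.5. The sign can reverse because the two rules then no longer count the same events.

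**Scale.** The standard error at n = 21 is sqrt(0.278 x 0.722 / 21) = 0.098, about 10 points.

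**The case against.** The strongest reply is that the sentence is meant for patients who are lost. Section 18.1 has a lost-to-follow-up form separate from the survival and disease-status form, and for truly lost patients the rule changes almost nothing. Patients still in contact have their disease status recorded every 6 months until progression, with documentation of progression. Section 11.45 asks for objective progression to be documented after treatment stops, and an exit scan is required. The no-capture scenarios therefore assume that a required form yields nothing. The 54-day gap lies within one 8-week scan interval.

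The differences above are also plan minus fix, not the plan's own error. In the worst case the plan is off by 31.7 - 27.8 = +3.9 and the fix by 24.5 - 27.8 = -3.3. With 4-16 months of follow-up the plan is the closer at 80% capture, and also at 50% capture in the second table (+0.5 against -1.7). At 36 months with no capture, the fix removes only 0.8 of a 4.6-point error. Finally, PFS is descriptive, and a shift of a point or two is small beside a standard error near 10.

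Most of this stands, and it limits the point. It does not rescue the wording. The plan does not confine the sentence to lost patients, the forms reduce hidden progressions without changing the censoring date, and a date last known alive remains the wrong date for this endpoint.

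**Conclusion.** The concern holds. Section 16.432b applies the overall-survival censoring date to PFS, and nothing elsewhere in the plan corrects it. Followed literally, it counts unassessed time as progression-free and, for the same events, can only raise the curve.

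The effect is small in most scenarios: at most 1.3 points on 12-month PFS with the full 36 months of follow-up, and negligible for patients truly lost. It becomes material only when a sizeable share leave imaging, stay in contact and have progressions that go unrecorded. Every size rests on assumed leaving rates, medians and capture, because the documents give none.

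The response endpoint and the decision rule in 16.42 are unaffected. This is a definition error in a named secondary endpoint that should be corrected, and no threat to the primary conclusion.

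**What to change.** Replace the censoring sentence in 16.432b with:

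> Patients alive without documented progression, including those progression-free at data cut-off, are censored at the date of the last adequate tumour assessment, on or off protocol, showing no progression (registration if there is none after baseline). Contact that only confirms the patient is alive is not an assessment.

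Keep last-known-alive censoring for overall survival only, and keep death from any cause as a PFS event. Report beside it, to be read together, a version that censors deaths after two or more consecutive missed assessments at the last adequate assessment. Record the date and result of off-protocol scans without progression as well, since the 18.1 footnote asks only for documentation of progression.

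The cost is one SAP sentence, one extra run and, if not already collected, one date field. The limits should be stated (12-month PFS, points from complete imaging):

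- **Short follow-up.** Leavers' deaths count while living leavers are censored early. At 4-16 months with no capture the fix is -3.3 to +0.3, the plan +0.7 to +5.3, and the late-death version -1.3 to +3.2. At 80% capture the plan is closer (-1.0 to +0.1, against -2.3 to -0.3).
- **Mature data.** At 36 months with no capture the fix still over-estimates by 1.1 to 7.0 (plan 1.4 to 7.6), mostly from deaths counted late. The late-death version is -1.3 to +3.2.
- **Negative off-protocol scans ignored.** If off-protocol progressions count but negative scans do not, the fix is -5.4 to -0.7 at 4-16 months with 80% capture. Hence the date field.
- **Informative leaving.** With the progression hazard doubled after leaving (20% assigned, no capture, 4-28 months), complete imaging gives 24.5-26.0%, the plan 29.0-31.0%, the fix 27.1-29.1% and the late-death version 26.8-29.5%. No choice of censoring date removes this bias.
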